### 1.3 Rationale for Study Conduct

Patients with GBM who have disease recurrence after initial treatment with surgery, RT, and temozolomide (first recurrence) have no curative options for treatment; and few therapies that have been shown to prolong survival. In this patient population, bevacizumab has demonstrated improved PFS-6, however, an OS benefit has not been shown. PDGFR $\alpha$  is known to be expressed in both newly diagnosed and recurrent GBM at consistent and high levels, but whether bevacizumab therapy alters PDGFR $\alpha$  expression is also unknown. Preclinical mouse xenograft studies with GBM cell lines have demonstrated that inhibition of PDGFR $\alpha$  signaling by MEDI-575 as a single agent can cause regression of tumors. This group of patients clearly needs additional therapies that may prolong survival and reduce the burden of disease.

Evaluating MEDI-575 in this patient population represents a rational and ethical approach to determine whether MEDI-575 has clinical activity against GBM. Available therapies either do not significantly prolong PFS or have not clearly demonstrated an improvement in OS. Treatment with MEDI-575 would not prevent subsequent treatment with either bevacizumab or a cytotoxic agent such as carmustine or temozolomide. Response rates and PFS-6 for therapies given subsequent to bevacizumab are not well understood and a single-arm trial in such a population would be difficult to size and evaluate. Anecdotal reports from investigators also suggest that patients become refractory to subsequent therapies after treatment with bevacizumab, but the reason for this is not known. Thus, given the choice between evaluation of MEDI-575 at first recurrence or second recurrence following bevacizumab, first recurrence is more likely to identify activity and will not prevent subsequent treatment with bevacizumab, which has been shown to prolong PFS-6. Moreover, there are no clinical or non-clinical data to suggest that treatment with MEDI-575 would prevent subjects from obtaining benefit with other subsequent therapies.

## **1.4 Benefit-Risk and Ethical Assessment**

The Phase 1 study of MEDI-575 (MI-CP187) in subjects with advanced solid tumors did not identify any significant risks. Most toxicities observed in the Phase 1 study were  $\leq$  Grade 2 in severity and SAEs were generally related to the subject's underlying disease and assessed as unrelated to MEDI-575. One SAE, pulmonary embolism (Grade 4), was assessed as possibly related to MEDI-575, although this interpretation is complicated by a previous history of pulmonary embolism prior to treatment with MEDI-575. Prolonged exposure to MEDI-575 has not been identified with any unique risks; however, prolonged exposure at the Phase 2 dose of 25 mg/kg every 3 weeks has not yet been evaluated. Together, these data suggest that MEDI-575 when used as a single agent is safe and does not represent an undue risk in this patient population.

Subjects to be treated in the current protocol have no available curative therapies, and standard therapies only provide a median OS of about 7 months ([Franceschi et al, 2009](#)). Even if MEDI-575 should prove to be ineffective, there are no clinical or non-clinical data to suggest that treatment with MEDI-575 would prevent subjects from obtaining benefit with other subsequent therapies. Therefore, evaluation of MEDI-575 at first recurrence of GBM is reasonable given the possibility of activity, the difficulty in evaluating activity in later lines, and the availability of subsequent therapies. Continued therapy in the absence of toxicity or progression should provide the maximum benefit to subjects enrolled in this trial.

## **2 Study Objectives**

### **2.1 Primary Objective**

The primary objective of this study is to evaluate the PFS-6 in adult subjects with a first recurrence of GBM who are treated with MEDI-575.

### **2.2 Secondary Objectives**

The secondary objectives of this study are:

- 1) To evaluate other antitumor activities of MEDI-575
- 2) To describe the safety and tolerability of MEDI-575
- 3) To determine the expression of PDGFR $\alpha$  in the tumor cells of archived tumor samples

## 2.3 Exploratory Objectives

The exploratory objectives of this study are:

- 1) To determine the immunogenicity of MEDI-575
- 2) To describe the PK of MEDI-575
- 3) To evaluate the biomarkers associated with MEDI-575 treatment
- 4) To evaluate intratumoral MEDI-575 levels in GBM following treatment
- 5) To investigate the effects of MEDI-575 on patient reported outcomes

[figure not shown]
## 3 Study Design

### 3.1 Overview of Study Design

This is a Phase 2, multicenter, open-label, single-arm study to evaluate the antitumor activity, safety, and pharmacology of MEDI-575 in adult subjects with first recurrence of GBM.

Approximately 55 subjects will be enrolled to determine the preliminary efficacy profile of MEDI-575 in the treatment of subjects with first recurrence of GBM. Subjects will receive MEDI-575 as a 60-minute IV infusion on Day 1 every 21 days until disease progression, initiation of alternative anticancer therapy, unacceptable toxicity, or other reasons for subject withdrawal (see Section 4.2.3) (Figure 3.1-1). In Cycle 2 and beyond, a dose can be delayed up to 7 days for unavoidable scheduling issues. MEDI-575 may be withheld for up to 21 days until resolution to  $\leq$  Grade 1 toxicity after agreement with the sponsor. The primary assessment of antitumor activity is PFS-6; progression will be determined using *Updated Response Assessment Criteria of High Grade Gliomas- Neuro-Oncology Working Group v.1* (see Appendix 5) (Wen et al, 2010). Approximately 15 investigational sites in the United States (USA) will participate in this study. Subjects who receive any amount of MEDI-575 and proceed to subsequent surgery as therapy for GBM (at second recurrence/disease progression) will be requested to allow use of surgically resected tissue for analysis of intratumoral levels of MEDI-575.

**Figure 3.1-1 Study Flow Diagram**

The endpoints to be measured in this study are described in Section 7.3.

### 3.2 Estimated Duration of Subject Participation

Administration of MEDI-575 may be continued based on the criteria described in Section 4.5.2. All subjects will be followed every 3 months for the duration of the trial (defined as 9 months from the date the last subject is entered into the trial or when the sponsor stops the study) until the criteria in Section 4.6 are met.

### 3.3 Study Stopping Criteria

If any of the following occur, administration of investigational product will be stopped and no additional subjects will be entered into the study:

- 1) Death in any subject in which the cause of death is assessed as related to investigational product
- 2) Anaphylactic reaction to investigational product in any subject
- 3) Other events that, in the judgement of the medical monitor, are deemed serious enough to warrant immediate review by the MedImmune Safety Monitoring Committee (SMC)
- 4) A DLT rate greater than 30% in the first 15 subjects enrolled in the study (see Section 4.5.4.2)

If any of the above-listed events occurs, a prompt cumulative review of safety data and the circumstances of the event in question will be conducted (see Section 6.5) to determine whether dosing and study entry should be resumed, whether the protocol will be modified, or whether the study will be discontinued permanently. Review and approval by the MedImmune SMC are required for resumption of the study in the event the study is

interrupted because of 1 of the above-listed events. Where applicable, regulatory authorities and Institutional Review Boards (IRB)/Independent Ethics Committees (IEC) will be notified of any study actions taken.

Any subjects who have already received investigational product and are currently in the study at the time study stopping criteria are met will continue to be followed by the investigator for safety.

Withdrawal criteria for individual subjects are provided in Section [4.2.3](#).

### **3.4 Rationale for Study Design, Doses, and Control Groups**

This is a multicenter, open-label, single arm, single agent study of MEDI-575 to determine the safety and antitumor efficacy of MEDI-575 in adult subjects with first recurrence of GBM. Progression free survival at 6 months (PFS-6) will be used to determine efficacy, and provides a direct measure of the effect of MEDI-575 on antitumor activity. Progression free survival or PFS-6 may correlate with OS, and prolongation of PFS may in itself be a measure of clinical benefit. Unlike OS, measurement of PFS is not confounded by subsequent therapies. Overall survival and ORR will be secondary endpoints. Response and progression will be measured using proposed criteria developed by the Response Assessment in Neuro-Oncology (RANO) Working Group (see [Appendix 4](#) and [Appendix 5](#)), which will be assessed by an independent radiographic analysis.

The choice of a single-arm trial is appropriate given this patient population and the goals of the study. MEDI-575 has not yet been evaluated in GBM. Patients with recurrent GBM have no curative therapies, and there is still a need for additional therapies for this population. A PFS-6 of 15-20% is generally accepted as demonstration of clinical activity in patients with first recurrence of GBM ([Ballman et al, 2007](#); [Prados, 2006](#)). In the absence of therapy, all patients who have a recurrence will continue to progress rapidly. A randomized trial would require comparison to another agent, or addition to another agent, and would require a large number of patients from a very limited pool. In this patient population with very limited therapeutic options and no firmly established standard of care, a single-arm trial is an acceptable design to evaluate the single-agent activity.

The Phase 2 dose (25 mg/kg every 21 days) is based on the ongoing Phase 1 first time in human study (MI-CP187), which evaluates the safety, tolerability, and antitumor activity of MEDI-575 in advanced solid tumors refractory to standard therapy. In MI-CP187, a standard

3+3 dose-escalation study, MEDI-575 was evaluated at doses up to 15 mg/kg once every 7 days and 25 and 35 mg/kg every 21 days. No DLTs were identified at any doses, demonstrating that MEDI-575 appears to be tolerable. The Phase 2 dose was chosen based on PK/pharmacodynamic modeling using preclinical pharmacology models, as well as analysis in the Phase 1 study.

In preclinical tumor xenograft studies, using lung cancer models, MEDI-575 demonstrated maximal activity at average intravascular concentrations of approximately 250 µg/mL. Higher concentrations did not result in superior antitumor activity. Glioblastoma multiforme models were the most sensitive to MEDI-575, demonstrating maximal activity at an approximately 10-fold lower dose than other solid tumor models. In the Phase 1 study of MEDI-575, a minimum trough concentration of 150 µg/ml resulted in maximal pharmacodynamic response, as measured by circulating PDGF-AA. Pharmacokinetic analysis demonstrates that at a dose of 9 mg/kg every 7 days or 25 mg/kg every 21 days, the serum trough concentration of MEDI-575 is expected to be above this value of 150 µg/mL throughout the dosing interval and the average concentration is at or above 250 µg/mL.

In general, large molecules such as monoclonal antibodies do not cross the blood brain barrier (BBB), which may pose difficulty in achieving adequate drug levels of MEDI-575 in the treatment of GBM. Despite this, there are preclinical and clinical data suggesting that sufficient drug levels may be achieved in this disease setting. Disruption of the BBB occurs in brain ischemia, malignancies, and neurodegenerative disorders including Alzheimer disease (Morita et al, 1999; Wolburg et al, 2003). Gliomas, particularly GBM, disrupt the BBB and cause brain edema that contributes to morbidity and mortality. Breakdown of the BBB and the formation of edema are well characterized hallmarks of brain tumors and are intrinsic to their pathogenesis and clinical effects (Stummer, 2007). Electronic microscopic studies have revealed that brain tumors induce tight-junction openings that become more pronounced with increasing malignancy (Nir et al, 1989). Tight-junction protein expression is altered *in situ* in anaplastic astrocytomas and GBM and *in vitro* treatment with GBM-derived factors, resulting in the disruption of the barrier function of brain-derived endothelial cells (Isihara, 2008). In one mouse model of Alzheimer's disease (Banks et al, 2007), a monoclonal immunoglobulin M has been shown to cross the BBB to target amyloid. At least two antibodies have been studied in humans for their ability to cross the BBB. In patients with multiple sclerosis, rituximab, which targets CD20 on B-cells, has been shown to be present in the cerebrospinal fluid (CSF) up to 24 weeks following systemic administration (Petereit, 2009). In another study, trastuzumab, which targets human epidermal growth factor 2 present on metastatic breast cancer, was shown to be present in the CSF following

systemic administration, and levels were increased with disruption to the BBB caused by radiotherapy (Stemmler et al, 2007). Although these data are not specific to GBM, they suggest that there is a reasonable likelihood that MEDI-575 will cross the BBB and be able to target tumors expressing PDGFR $\alpha$ , especially in the setting of a disrupted BBB occurring in GBM.

## **4 Study Procedures**

### **4.1 Subject Participation and Identification**

Study participation begins once written informed consent is obtained (see Section 10.3 for details). Once informed consent is obtained, a subject identification (SID) number will be assigned by a central interactive web response system (IWRS), and the screening evaluations may begin to assess study eligibility (inclusion/exclusion criteria). The SID number will be used to identify the subject during the screening process and throughout study participation, if applicable.

A master log of all consented subjects will be maintained at the site and will document all screening failures (ie, subjects who are consented but do not meet study eligibility criteria and are not entered), including the reason(s) for screening failure (see Section 9.1 for details).

### **4.2 Subject Selection and Withdrawal**

The subjects in this study will be adults with first recurrence of GBM (Stage IV malignant glioma) following first-line therapy of temozolomide and radiation. The investigator (physician) or qualified designee will discuss the study with a subject/legal representative of a subject who is considered a potential candidate for the study and provide the subject/legal representative with the study-specific informed consent form(s) approved by the IRB/IEC. The investigator or designee will address any questions and/or concerns that the subject/legal representative may have and, if there is continued interest, will secure written informed consent for participation in the study. Written informed consent and any locally required authorization (eg, Health Insurance Portability and Accountability Act [HIPAA] authorization in the USA and European Union [EU] Data Privacy Directive authorization in the EU), will be obtained prior to conducting any protocol-specific procedures, including screening evaluations or medication washouts. See Section 10.3 for additional details concerning informed consent.

#### 4.2.1 Inclusion Criteria

Subjects must meet *all* of the following criteria:

- 1) Written informed consent and HIPAA authorization (applies to covered entities in the USA only) obtained from the subject/legal representative prior to performing any protocol-related procedures, including screening evaluations
- 2) Age  $\geq 18$  years old at the time of screening
- 3) Histologically confirmed diagnosis of World Health Organization Grade IV malignant glioma (glioblastoma or gliosarcoma)
- 4) Previous first line treatment with radiotherapy and temozolomide (treatment prior to radiation and temozolomide permitted, [ie, Gliadel])
- 5) Documented first recurrence of GBM by diagnostic biopsy or by contrast-enhanced magnetic resonance imaging (MRI) as per *Updated Response Assessment Criteria of High Grade Gliomas- Neuro-Oncology Working Group* (see [Appendix 5, Wen et al, 2010](#))
- 6) Eastern Cooperative Oncology Group (ECOG) performance status of 0 or 1 (see [Appendix 1](#))
- 7) Life expectancy  $\geq 12$  weeks
- 8) Prothrombin time elevation  $\leq$  Grade 2 is acceptable for subjects on anticoagulant therapy
- 9) Adequate hematologic function defined as:
  - Hemoglobin  $\geq 10$  g/dL
  - Absolute neutrophil count (ANC)  $\geq 1500/\text{mm}^3$
  - Platelet count  $\geq 100,000/\text{mm}^3$
- 10) Adequate organ function defined as follows:
  - Aspartate aminotransferase (AST) and alanine aminotransferase (ALT)  $\leq 2 \times$  institutional upper limit of normal (ULN);
  - Bilirubin  $\leq 1.5 \times$  ULN except in the case of subjects with documented or suspected Gilbert's disease  $\leq 5 \times$  ULN;
  - Calculated creatinine clearance (CrCl)  $\geq 50$  mL/min as determined by the Cockcroft-Gault equation ([Cockcroft and Gault, 1976](#))
- 11) Provide consent to allow collection of archived tumor samples
- 12) Negative serum beta human chorionic gonadotropin ( $\beta$ HCG) test (women only)

- 13) Women of childbearing potential, unless surgically sterile (including tubal ligation) or at least 1 year post menopause, must have used 2 effective methods of avoiding pregnancy (including oral, transdermal, or implanted contraceptives, intrauterine device, female condom with spermicide, diaphragm with spermicide, cervical cap, abstinence, use of a condom with spermicide by the sexual partner, or sterile sexual partner) from the time of signing the informed consent, and must agree to continue using such contraceptive precautions for 90 days after the final dose of investigational product; cessation of birth control after this point should be discussed with a responsible physician
- 14) Men unless surgically sterile, with their female partners (unless surgically sterile or 1 year post menopause) must use 2 effective methods of birth control as described in Criterion 13 above and must agree to continue using such contraceptive precautions from Cycle 1, Study Day 1 through 90 days after the final dose of investigational product

#### **4.2.2 Exclusion Criteria**

Any of the following would exclude the subject from participation in the study:

- 1) Treatment with any investigational agent 30 days prior to study entry
- 2) Concurrent enrollment in another clinical study involving an investigational agent
- 3) Employees of the clinical study site or any other individuals involved with the conduct of the study, or immediate family members of such individuals
- 4) Any chemotherapy, radiotherapy, immunotherapy, biologic, or hormonal therapy for treatment of cancer within 30 days prior to study entry
- 5) Previous mAb treatment specifically directed against PDGF or PDGF receptors
- 6) Previous bevacizumab or other VEGF and anti-angiogenic treatment
- 7) More than 1 recurrence of GBM
- 8) Any surgery (not including minor diagnostic procedures) within 2 weeks prior to baseline disease assessments; or not fully recovered from any side effects of previous procedures
- 9) History of serious allergy or reaction to any component of the MEDI-575 formulation
- 10) New York Heart Association  $\geq$  Grade 2 congestive heart failure within 6 months prior to study entry (see [Appendix 3](#))
- 11) Uncontrolled or significant cardiovascular disease, including:
  - Myocardial infarction and transient ischemic attack or stroke within 6 months prior to enrollment
  - Uncontrolled angina within 6 months

- Diagnosed or suspected congenital long QT syndrome
  - Any history of clinically significant ventricular arrhythmias (such as ventricular tachycardia, ventricular fibrillation, or Torsades de pointes);
  - Clinically significant abnormality on electrocardiogram (ECG)
- 12) History of other invasive malignancy within 5 years prior to study entry except for cervical carcinoma *in situ* (CIS), non-melanomatous carcinoma of the skin or ductal carcinoma *in situ* (DCIS) of the breast that have been surgically cured
  - 13) Any evidence of active infection requiring the use of systemic antimicrobial treatment within 72 hours prior to initial treatment with MEDI-575
  - 14) History of active human immunodeficiency virus or active hepatitis B or C viral infection will be excluded to eliminate the risk of increased AEs due to immune compromise.
  - 15) Systemic immunosuppressive therapy. Subjects taking corticosteroids must be on a stable dose for 7 days prior to initiation of treatment with MEDI-575
  - 16) Presence of extracranial metastatic or leptomeningeal disease
  - 17) Pregnancy or lactation
  - 18) Previous medical history or evidence of an intercurrent illness that may, in the opinion of the investigator, compromise the safety of the subject in the study
  - 19) Any physical, social, or psychiatric condition, which would prevent effective cooperation or participation in the study
  - 20) Any condition that, in the opinion of the investigator, would interfere with evaluation of the investigational product or interpretation of subject safety or study results
  - 21) Patients who can not safely undergo MRI due to pacemakers, metal implants, infusion catheters or other metal device.

#### **4.2.3 Withdrawal Criteria**

An individual subject will not receive further treatment if any of the following occur in the subject in question:

- 1) Withdrawal of consent or lost to follow-up
- 2) Adverse event that, in the opinion of the investigator or medical monitor, contraindicates further dosing
- 3) Subject is determined to have met 1 or more of the exclusion criteria for study participation
- 4) Pregnancy

**Withdrawal of consent:** If consent is withdrawn, the subject will not receive any further treatment or further study observation. Note that the subject may need to undergo additional tests or tapering of treatment to withdraw safely.

**Lost to follow-up:** Subjects will be considered lost-to-follow-up only if no contact has been established by the time the study is completed such that there is insufficient information to determine the subject's status at the end of study (defined as 9 months from the date the last subject is entered into the trial or when the sponsor stops the study).

- Note: Subjects refusing to return to the site or to continue participation in the study should be documented as “withdrawal of consent” rather than “lost to follow-up.” Investigators should document attempts to re-establish contact with missing subjects throughout the study period. If contact with a missing subject is re-established, the subject should not be considered lost-to-follow-up and any evaluations should resume according to the protocol

**Permanent discontinuation of treatment:** Subjects who are permanently discontinued from further receipt of treatment, regardless of the reason (withdrawal of consent, due to an AE, other), will be identified as having permanently discontinued treatment. Subjects who permanently discontinue treatment may either be considered to have completed the study or not to have completed the study (see Section 4.6).

Subjects who are permanently discontinued from receiving treatment will be followed for safety through 90 days after the last dose of treatment, including the collection of any protocol-specified blood or urine specimens, unless the subject withdraws consent, is lost to follow-up, or has enrolled in another clinical study.

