## **5.2 Schedule of Study Procedures**

All subjects who are assigned an SID number and receive any treatment will be followed according to the protocol regardless of the number of doses received, unless consent is withdrawn. The investigator must notify the sponsor or designee of deviations from protocol visits or evaluations and these evaluations, if applicable, must be rescheduled or performed at the nearest possible time to the original scheduled visit. Protocol deviations will be recorded in the source document with an explanation for the deviation and any study-specific electronic case report forms (eCRFs) or logs designated for capturing protocol deviations, if

applicable for the study. The investigator must comply with the applicable requirements related to reporting of protocol deviations to the IRB/IEC.

Subjects/legal representatives will be instructed to call study personnel to report any abnormalities during the intervals between study visits and to come to the study site if medical evaluation is needed and the urgency of the situation permits. For emergency and other unscheduled visits to a medical facility other than the study site, medical records will be obtained by the investigator and made available to the sponsor or designee during monitoring visits.

Schedules of study procedures for the screening and treatment period as well as the follow-up period are presented in [Table 5.2-1](#) and [Table 5.2-2](#) , respectively, followed by a description of each visit. A description of the study procedures is included in [Section 5.3](#)

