### **5.2.6.3 Every 3 Months (Plus or Minus 14 Days) After Last Treatment**

The following evaluations will be performed every 3 months ( $\pm$  14 days) after the last treatment as specified (for subjects who discontinue treatment due to reasons other than disease progression or initiation of alternative anticancer therapy, these evaluations will be performed until documentation of disease progression, initiation of alternative anticancer therapy, or the end of study [defined as 9 months post the date the last subject is entered on the trial or when sponsor stops the study]):

- 1) Evaluation of disease
  - MRI scan
  - Focused physical examination
  - ECOG performance status

- 2) Blood collection for anti-MEDI-575 antibodies (3-month post visit only)
- 3) Survival status and subsequent anticancer therapy must be collected in every subject regardless of the reason for treatment discontinuation. Assessment can be either performed on a clinic visit or telephone contact until death or the end of the study

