Progression	
Defined by any of the following: <math>\geq 25\%</math> increase in sum of the products of perpendicular diameters of enhancing lesions compared with the smallest tumor measurement obtained either at baseline (if no decrease) or best response, on stable or increasing doses of corticosteroids*; significant increase in T2/FLAIR nonenhancing lesion on stable or increasing doses of corticosteroids compared with baseline scan or best response after initiation of therapy* not caused by comorbid events (eg, radiation therapy, demyelination, ischemic injury, infection, seizures, postoperative changes, or other treatment effects); any new lesion; clear clinical deterioration not attributable to other causes apart from the tumor (eg, seizures, medication adverse effects, complications of therapy, cerebrovascular events, infection, and so on) or changes in corticosteroid dose; failure to return for evaluation as a result of death or deteriorating condition; or clear progression of nonmeasurable disease.

Note: All measurable and nonmeasurable lesions must be assessed using the same techniques as at baseline.

Abbreviations: MRI, magnetic resonance imaging; FLAIR, fluid-attenuated inversion recovery.

\*

Stable doses of corticosteroids include patients not on corticosteroids.

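### Section 4.2.3 records refusal of site visits as withdrawal of consent and so ends observation, in conflict with the survival follow-up in 5.2.6.3; OS can be overstated if sites follow 4.2.3

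*Protocol*

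**What the plan says.** The relevant text is spread over several parts of the protocol.

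- **Section 4.2.3, note on lost to follow-up.** "Subjects refusing to return to the site or to continue participation in the study should be documented as" withdrawal of consent, and not as lost to follow-up.
- **Section 4.2.3, withdrawal of consent.** "If consent is withdrawn, the subject will not receive any further treatment or further study observation". Nothing here exempts survival status.
- **Section 5.2.** Treated subjects are to be "followed according to the protocol regardless of the number of doses received, unless consent is withdrawn".
- **Section 4.6.** Subjects who withdrew consent count as not having completed the study.
- **Section 5.2.6.3.** "Survival status and subsequent anticancer therapy must be collected in every subject regardless of the reason for treatment discontinuation". On the mode of contact: "Assessment can be either performed on a clinic visit or telephone contact until death or the end of the study".
- **Section 4.2.3, permanent discontinuation.** Withdrawal of consent is itself listed as a reason for stopping treatment: "regardless of the reason (withdrawal of consent, due to an AE, other), will be identified as having permanently discontinued treatment".
- **Section 7.3.2.1.** OS is censored at the last date known alive for subjects who are alive at the end of the study or lost to follow-up. Withdrawal of consent is not named. PFS is censored at the last progression-free tumor assessment for subjects alive without documented progression before dropout.
- **Appendix 4.** The definition of progression includes "failure to return for evaluation as a result of death or deteriorating condition".

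**The concern.** Refusing to travel and refusing all contact are different decisions, and the note in 4.2.3 merges them. In recurrent GBM, a subject who stops attending is often one who is getting worse. If that subject is closed out as withdrawn, a death that a telephone call could have established is never recorded, and the OS time is censored shortly before the event. Kaplan-Meier then treats the subject as having the same prognosis as those still followed, which pushes the curve up. With one arm and about 55 subjects, no control group shares the bias and each lost death carries weight. An analysis plan cannot repair this afterwards, because the deaths would not be in the database.

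**Working it through.** **1. The instructions side by side.** Take a subject who declines further site visits but would accept a telephone call.

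- Under the 4.2.3 note the subject is recorded as having withdrawn consent. The withdrawal paragraph of 4.2.3 and the exception in 5.2 then stop observation.
- Under 5.2.6.3 survival status must still be collected, whatever the reason for stopping treatment. Since 4.2.3 lists withdrawal of consent among those reasons, the sentence covers this subject too.

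One section orders the call and two end observation. A site holding a recorded withdrawal of consent could reasonably make no contact; another could reasonably telephone.

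**2. The OS rule.** Section 7.3.2.1 names two censoring situations. The 4.2.3 note takes refusers out of the lost-to-follow-up group, and a refuser whose status is unknown is not known to be alive at the end of the study. The rule therefore does not name these subjects.

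**3. Illustrated size for OS.** The protocol gives no figure for this effect. Inputs:

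- Median OS of about 7 months (Section 1.4).
- Drop-out of 10% (Section 7.5), not split by reason.
- Assumptions: exponential survival; a share f of 5% or 10% of all subjects closed out 0.5 to 1.5 months before death, whenever death falls. With 55 subjects that is 0.05 × 55 = 2.75 to 0.10 × 55 = 5.5 subjects.

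As the lead time shrinks to zero, the observed death hazard is (1 − f) times the true one, so the Kaplan-Meier median tends to 7/(1 − f). That gives 7/0.95 = 7.37 months and 7/0.90 = 7.78 months. Large-sample simulation with the stated lead times gives:

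| Share f | Median OS (true 7.0 months) | 6-month OS (true 0.5^(6/7) = 55%) |
|---|---|---|
| 5% | about 7.3 months | about 57% |
| 10% | about 7.7 months | about 58% |

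**4. PFS and PFS-6.** Under Appendix 4, a subject who does not return because of deterioration has progressed, which is a PFS event. If that is applied, the bias in PFS-6 from this route is about zero. It appears only if the withdrawal label replaces the reason for non-return and the 7.3.2.1 dropout censoring is used. This can happen: 7.3.2.1 does not refer to the Appendix 4 rule, and 5.3.7 uses blinded central imaging review for progression, for which a missed visit supplies no scan.

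In that case only, with f = 10% censored at the preceding 6-weekly scan (Section 5.2.4), a true PFS-6 of 16% reads about 18.5% and a true 30% about 33.4%. With 55 subjects and a true rate of 16%, the chance that the lower 90% limit reaches 16% rises from 4.9% to 11.3% with a log-log interval, or from 2.4% to 9.0% with a linear one. The protocol does not say which interval form applies.

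**The case against.** The strongest reply is that 5.2.6.3 already settles the matter: survival is required in every subject, a telephone call is enough, and withdrawal of consent is among the discontinuation reasons it covers. A reader might infer from 4.2.3 alone that survival data are certain to be lost; 5.2.6.3 does not support that. What stands is a contradiction, and a site cannot tell from the text which instruction prevails.

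A reader might also infer that PFS-6, and with it the success criterion, is overstated. Appendix 4 answers this directly, because the declining subject who stops attending meets its definition of progression. Sequence weakens the inference further. Under an exponential model a PFS-6 of 16% implies a median PFS of about 6 × ln 2 / −ln 0.16 = 2.3 months, against a median OS of about 7 months, so much terminal decline would come after a PFS event has been recorded.

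Larger OS shifts can be produced. If all of the 10% drop-out were declining subjects who would have died before month 6, the median would read 8.2-8.3 months and 6-month OS 62-63%. Nothing in the protocol supports concentrating every drop-out in that group.

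Finally, OS has no stated historical comparator or test. The null rate and decision rule in 7.5 concern PFS-6 alone, so the consequence for OS is a biased secondary estimate and not a wrong study decision.

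**Conclusion.** The point holds as an internal contradiction with a plausible upward bias in OS. Sections 4.2.3 and 5.2 end observation for anyone who refuses site visits, 5.2.6.3 requires survival status from the same subjects, and the OS censoring rule does not name them. If sites follow 4.2.3, median OS of 7.0 months could read about 7.3-7.7 months. This assumes that 5-10% of subjects are affected, that survival is exponential and that close-out comes 0.5-1.5 months before death. The direction is plausible; the share, and how many of these subjects could still be reached, is not known from the protocol. For PFS and PFS-6 the exposure is conditional on dropout censoring displacing the Appendix 4 rule. The documents do not establish that either endpoint will be overstated.

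**What to change.** Replace the note in 4.2.3 with two categories:

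- **(a) Declines treatment and/or site visits.** This is not withdrawal of consent. Follow-up for survival and subsequent therapy continues under 5.2.6.3 by telephone or medical record, and the reason for non-return is recorded.
- **(b) Explicitly withdraws consent to all follow-up.** Contact stops.

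Then align the rest of the protocol:

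- Limit the consent exception in 5.2 and the non-completion rule in 4.6 to category (b).
- Name category (b) in the OS censoring rule of 7.3.2.1, censored at the last date known alive.
- Make the PFS dropout censoring in 7.3.2.1 refer to the Appendix 4 rule on failure to return, so that the recorded reason decides between event and censoring.

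The cost is amendment and consent-form wording and one CRF item. Telephone follow-up is already planned, so no visits are added.
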